12.1 Adverse Events

A TEAE is defined as any AE with a start date/time on or after the date/time of the first injection (Baseline/Day 1) through the last study visit (follow-up visit), whether or not it is considered causally related to the study drug.

Treatment Emergent/Non-Treatment Emergent:

- Complete Missing Dates:
 - If both the start date and the end date are totally missing, then the AE is assumed to be treatment emergent.
- Partial Missing Dates:
 - If the start date is missing and the non-missing end date is prior to first injection (Baseline/Day 1) date, then the AE is not considered treatment emergent.

- If the start date is missing and the partial end date can be assumed to be prior to first injection (Baseline/Day 1) date (month and/or year before infusion date), then the AE is not considered treatment emergent.
- If the start date is missing and the end date is after the first injection (Baseline/Day 1) date or the partial end date cannot be assumed to be prior to the first injection (Baseline/Day 1) date (based on month and/or year), then the AE is assumed to be treatment emergent.
- If the start date is partial and can be assumed to be prior to the first injection (Baseline/Day 1) date (based on the month and/or year) and the non-missing end date is prior to the injection date, then the AE is not considered treatment emergent.
- If the partial start date cannot be assumed to be prior to the first injection (Baseline/Day 1) date, then the AE is assumed to be treatment emergent.
- Complete Dates:
 - If the start date is prior to the first injection (Baseline/Day 1) date, then the AE is not considered treatment emergent.
 - If the start date is equal to the first injection (Baseline/Day 1) date and the start time is missing, then the AE is considered treatment emergent.
 - If the start date is equal to the first injection (Baseline/Day 1) date and the start time is prior to the first injection time, then the AE is not considered treatment emergent.
 - If the start date is equal to the first injection (Baseline/Day 1) date and the start time is on or after the first injection time, then the AE is considered treatment emergent.
 - If the start date is after the first injection (Baseline/Day 1) date, then the AE is considered treatment emergent.

For the imputation of missing start or end dates, the rules stated in Section 4.1 will be followed.

All AEs will be coded according to MedDRA 24.1 or higher.

12.1.1 Incidence of Adverse Events

An overall summary table with count and percentage of subjects with TEAEs and count of events will include:

- TEAEs
- TEAEs by greatest severity
- TEAEs by closest relationship to study drug
- TEAEs by closest relationship to study procedures

- TEAEs leading to treatment discontinuation
- TEAEs leading to study discontinuation
- TEAEs of special interest
- TEAEs of special interest by greatest severity
- TEAEs due to COVID-19
- Asthma-related TEAEs adjudicated by IAC
- Asthma-related TEAEs adjudicated by IAC by greatest severity
- Asthma-related TEAEs adjudicated by IAC by closest relationship to study drug
- Serious TEAEs (both fatal and non-fatal)
- Non-fatal serious TEAEs
- TEAEs leading to death
- Serious TEAEs by closest relationship to study drug
- Serious TEAEs by closest relationship to study procedures
- Serious TEAEs leading to treatment discontinuation
- Serious TEAEs leading to study discontinuation

The incidence of AEs will be summarized in tables with count and percentage of subjects with AEs and count of events by system organ class (SOC) and preferred term (PT). Unless otherwise specified, at each level of SOC or preferred term, a subject with multiple events will only be counted once per SOC or preferred term. AEs will be displayed by treatment for the Safety Set.

The following categories of AE will be summarized by SOC and PT:

- TEAEs
- TEAEs by greatest severity
- TEAEs related to study drug
- TEAEs related to study procedures
- TEAEs leading to treatment discontinuation
- TEAEs leading to study discontinuation
- TEAEs of special interest
- TEAEs of special interest by greatest severity
- TEAEs due to COVID-19
- Asthma-related TEAEs adjudicated by IAC

- Asthma-related TEAEs related to study drug adjudicated by IAC
- Asthma-related TEAEs reported by Investigator with adjudication outcome by IAC
- Asthma-related TEAEs related to study drug reported by Investigator with adjudication outcome by IAC
- Asthma-related TEAEs adjudicated by IAC by greatest severity
- Asthma-related TEAEs related to study drug adjudicated by IAC by greatest severity
- Serious TEAEs (both fatal and non-fatal)
- Non-fatal serious TEAEs
- TEAEs leading to death
- Serious TEAEs related to study drug
- Serious TEAEs related to study procedures
- Serious TEAEs leading to treatment discontinuation
- Serious TEAEs leading to study discontinuation

At each level of SOC or PT, if a subject experiences more than 1 occurrence of the same AE, the occurrence with the greatest severity, the closest relationship with the study drug and the closest relationship with the study procedures will be used in the corresponding summary tables. All AEs will be presented in tables in descending order from the SOC with the highest total incidence (across all treatment groups) to the SOC with the lowest total incidence. Within each SOC, AEs will be sorted in descending order of PT based on the total of all treatment groups.

TEAEs, TEAEs leading to death, serious TEAEs, non-fatal serious TEAEs, severe TEAEs, TEAEs of special interest, TEAEs leading to treatment discontinuation, TEAEs leading to study discontinuation and TEAEs due to COVID-19 will be listed separately.

Pre-treatment AEs (PTAEs) will be listed separately.

12.1.2 Relationship of Adverse Events to Study Drug and/or Study Procedures

The investigator is to determine whether there is a reasonable causal relationship between the occurrence of the AE and exposure to the study drug (i.e., nemolizumab or placebo) and/or study procedures (e.g., injection, topical background therapy, blood sample collection). Medical judgment should be used to determine the relationship, considering all relevant factors including the pattern of the reaction, temporal relationships, relevant medical history, and confounding factors such as co-medication or concurrent diseases.

The relationship assessment for an AE is to be completed using the following definitions for all AEs occurring during this clinical study:

- **Reasonable Possibility:** According to the reporting investigator, there is a reasonable possibility (i.e., suggestive evidence or arguments) that there is a causal relationship irrespective of the dose administered between the study drug and the AE, and/or between the clinical study protocol procedures (e.g., injection, topical background therapy, blood sample collection) and the AE.
- **No Reasonable Possibility:** No suggestive evidence or arguments can be identified regarding a causal relationship between the study drug or the clinical study protocol procedures and the AE.

If the relationship to study drug information is missing, then the corresponding AE is assumed to be related with reasonable possibility to the study drug. If a subject experiences more than 1 occurrence of the same AE, the occurrence with the closest relationship to study drug will be used in summary tables.

12.1.3 Severity of Adverse Event

Each AE will be assigned a category by the investigator as follows:

- **Mild:** An AE that is easily tolerated by the subject, causes minimal discomfort, and does not interfere with everyday activities.
- **Moderate:** An AE that is sufficiently discomforting to interfere with normal everyday activities; intervention may be needed.
- **Severe:** An AE that prevents normal everyday activities; treatment or other intervention usually needed.

If the severity is missing, then the AE is assumed to be severe. If a subject experiences more than 1 occurrence of the same AE, the occurrence with the greatest severity will be used in summary tables.

12.2 Clinical Laboratory Evaluations

Clinical laboratory evaluations will be performed according to the schedule of assessments in [Appendix A](#).

The safety laboratory assessments include the following parameters:

Hematology:

- Hemoglobin (g/L)
- Hematocrit (L/L)
- White blood cell count (with differential including eosinophils) ($10^9/L$)
- Red blood cell count ($10^{12}/L$)
- Platelet count ($10^9/L$)
- Erythrocytes Mean Corpuscular Volume (fL)

Urinalysis:

- pH
- Bacteria
- Glucose
- Casts
- Crystals
- Epithelial Cells
- Erythrocytes
- Ketones
- Occult Blood
- Protein
- Leukocytes
- Leukocytes Esterase
- Mucous Threads
- Nitrites
- Bilirubin
- Urobilinogen
- Specific gravity
- Yeast Cells

Serum chemistry:

- Creatinine (umol/L)
- Aspartate Amino Transferase (AST) (U/L)
- Alanine Amino Transferase (ALT) (U/L)
- Gamma glutamyltransferase (U/L)
- Alkaline Phosphatase (U/L)
- Lactate Dehydrogenase (U/L)
- Total Bilirubin (umol/L)
- Direct Bilirubin (umol/L)
- Albumin (g/L)
- Total Protein (g/L)
- Urate (mmol/L)
- Sodium (mmol/L)
- Potassium (mmol/L)
- Calcium (mmol/L)
- Chloride (mmol/L)
- Glucose (mmol/L)
- Urea Nitrogen (mmol/L)
- Total Cholesterol (mmol/L)
- Triglycerides (mmol/L)
- Low-density lipoprotein (LDL) Cholesterol (mmol/L)

- High-density lipoprotein (HDL) Cholesterol (mmol/L)
- Creatine Kinase (CK) (U/L)

Summary statistics of the observed values and change from baseline for all laboratory parameters will be provided by visits and treatment groups.

For quantitative parameter, results will be presented for each parameter by treatment in a shift table, using above, below, within normal range, between baseline and visits at Week 4, Week 8, Week 12 and Week 20. Results will be presented for each parameter by treatment group in a shift table, using normal, abnormal not clinically significant and abnormal clinically significant categorization based on the current version of Central Lab Manual and Alert Report Specification, between baseline and visits at Week 4, Week 8, Week 12 and Week 20.

Last post-baseline and worst post-baseline results (derived using both scheduled and unscheduled measurements) will also be included in summaries and shift tables. For each parameter, worst post-baseline value will be defined as the highest or lowest value relative to the reference range.

All post-baseline (both scheduled and unscheduled) measurements will be used for Potentially Clinically Significant Values (PCSV) determination (criteria are available in [Appendix D](#)).

Number and proportions of subjects with Potentially Clinically Significant Values will be summarized by visits and treatment groups.

All laboratory data will also be presented in listings for each parameter with abnormal values, clinically significant values and potentially clinically significant values (PCSV) flagged. Moreover, abnormal values and potentially clinically significant values will be presented in separate listings.

For statistical or graphical summaries of the laboratory tests, values above or below the limit of detection will be substituted with the lower limit of detection minus 1%, or the upper limit of detection plus 1% (e.g. '<3' is substituted by 2.97). In the data listings, the values are shown including the '<' or '>' sign.

Boxplots presenting the distribution of AST, ALT, ALP, Total Bilirubin and CPK over the visits will be displayed by treatment. An additional boxplot will be presented on the figure considering the maximum post-baseline value. Additionally, individual plots presenting the distribution of AST, ALT, ALP, Total Bilirubin and CPK, for subjects with abnormal values, over the visits will be displayed by treatment. An evaluation of drug-induced serious hepatotoxicity (eDISH) plot will be displayed in addition.

12.3 Pregnancy Testing

Pregnancy tests will be performed on female subjects of child-bearing potential. Serum pregnancy tests will be performed at all visits according to the schedule of assessments summarized in [Appendix A](#). Pregnancy test results will be presented in a listing.

12.4 Virology

Virology including Hepatitis B Surface Antigen (HBsAg), Hepatitis B Core Antibody (HBcAb), Hepatitis C Virus (HCV), HIV-1, and HIV-2 antibody will be assessed at the screening visit. Subjects with a positive HBcAb and a negative HBsAg will also be assessed for hepatitis B surface antibody. Subjects with positive HCV antibodies will have a confirmatory test for HCV (e.g. Polymerase Chain Reaction (PCR) test). These data will be presented in a listing.

12.5 Tuberculosis (TB) Testing

Immunosuppressant biologic treatments have been shown to increase the risk of TB infection or to cause conversion from latent to active TB in some circumstances. Because of this, subjects will be screened for active or latent TB before entry into this study. The data will be presented in a listing.

12.6 Vital Sign Measurements

Vital signs including pulse rate (beats/min), systolic and diastolic blood pressure (mmHg), body temperature (C), pre-dialysis weight (kg) and post-dialysis weight (kg) will be assessed over time during the study according to the schedule of assessments in [Appendix A](#). Descriptive statistics of observed values and change from baseline will be summarized by visit and by treatment.

Results from overall interpretation of vital signs assessments will be summarized by visit and treatment group and will be presented by treatment group in a shift table, using normal, abnormal not clinically significant and abnormal clinically significant categorization, between baseline and visits at Week 4, Week 8, Week 12 and Week 20.

All post-baseline (both scheduled and unscheduled) measurements will be used for Potentially Clinically Significant Values (PCSV) determination (criteria are available in [Appendix E](#)).

Number and proportions of subjects with Potentially Clinically Significant Values will be summarized by visits and treatment groups.

A corresponding listing with potentially clinically significant values (PCSV) flagged will also be provided.

12.7 Physical Examination

A complete physical examination including assessments of the head, ears, eyes, nose, throat, neck (including thyroid), skin/integumentary system, cardiovascular system, respiratory system, gastrointestinal system, musculoskeletal system, lymph nodes, nervous system, and extremities will be performed at screening, baseline/Day 1, and

subsequent scheduled visits. All physical examinations will be summarized in a table by visit and by treatment group. Results of physical examinations are categorized into normal, abnormal, and not done. If abnormal, results will be categorized with or without clinical significance. A corresponding listing will be provided with abnormal values flagged.

12.8 Electrocardiogram

A 12-lead ECG will be performed at specific visits according to the schedule of assessments in [Appendix A](#). Electrocardiogram results are categorized into normal, and abnormal. If abnormal, results will be categorized with or without clinical significance. Results will be summarized by visit and treatment group and will be presented by treatment group in a shift table, using normal, abnormal not clinically significant and abnormal clinically significant categorization, between baseline and visit at Week 12. Heart rate (beats/min) and PR, QRS, RR, QT, QTcB and QTcF intervals (msec) and their changes from baseline will be summarized by visit and treatment group. A corresponding listing will be provided with abnormal values flagged.

12.9 Respiratory Assessments

PEF and ACT will be performed according to subjects' asthma history as follows:

- 1) If subjects have no asthma history, PEF will be performed at Screening and Baseline.
- 2) If subjects have asthma history, PEF and ACT will be performed at all visits according to the schedule of assessments in [Appendix A](#).
- 3) If subjects have a new (de novo) diagnosis of asthma PEF and ACT will be performed at all subsequent visits (considering that some subjects will have performed some PEF testing at prior visits as per point 1).

ACT and PEF (observed values and changes from baseline) will be summarized by visit and treatment group. A corresponding listing will be also provided for both assessments.

For ACT, the numbers and percentages of subjects with an ACT score ≤ 19 will be summarized by visit and treatment group.

For PEF, the numbers and percentages of subjects with PEF $< 80\%$ of the predicted value will be presented by visit and treatment group and percent change from baseline will be classified as follows

- $\leq -20\%$
- $\leq -15\%$ and $> -20\%$
- $\leq -10\%$ and $> -15\%$
- $< 0\%$ and $> -10\%$
- $\geq 0\%$ and $< 10\%$

- $\geq 10\%$ and $< 15\%$
- $\geq 15\%$ and $< 20\%$
- $\geq 20\%$

and will be presented by visit and treatment group.

All PEF summaries will be presented for subjects with/without asthma history.

Additionally, individual plots presenting the distribution of ACT and PEF for subjects with abnormal values, over the visits will be displayed by treatment.

A listing with all known asthma triggers will be provided.

13 Independent Data Monitoring Committee

An Independent Data Monitoring Committee (IDMC) will review and monitor subject safety throughout the study. The IDMC will provide recommendations on the safety of subjects.

Details on the IDMC, including the plan of analysis for IDMC outputs, the composition of the IDMC, the procedures, roles, responsibilities, and their communications are provided in the IDMC charter.

14 Interim Analysis

No interim analysis is planned for this study.

15 Dose Selection

Dose selection will be based on the final analysis by evaluating the optimal risk-benefit and considering the potential impact of body weight.

CCI

A large black rectangular redaction box covers the majority of the page content below the 'CCI' label, starting from the 'Safety assessment' section and extending down to the page footer.

Safety assessment

The IDMC will review and monitor subject safety throughout the study.

16 Changes from the Protocol Analysis Plan

Any change from the protocol will be justified and fully documented.

If the blind review suggests changes to the principal features stated in the protocol, these have to be documented in a protocol amendment. Otherwise, it will suffice to update the statistical analysis plan with the considerations suggested from the blind review.

No changes have been made to the intent of protocol text.

The following clarification has been made:

- Addition of [Appendix C](#) for details about Multiple Imputation and Tipping Point analysis. Note that this clarifies that the tipping point approach is using the delta-adjustment multiple imputation framework under Missing Not at Random (MNAR) assumption.

17 General Features of Tables, Listings and Figures

TLF have to be printed in A4 page size with landscape orientation and with the following margins:

- Top: 2.0 cm (i.e. headers at 2.0 cm from page edge)
- Bottom: 2.0 cm (i.e. footers at 2.0 cm from page edge)
- Left: 0.8 cm
- Right: 0.8 cm

Courier New, 8-point font will be used for TLF contents (excluding column headers) and TLF footnotes.

Courier New, 8-point, bold font will be used for page headers and footers, TLF title, TLF headers, column headers and figures' axis labels.

A clear, accurate and complete programming code will be developed to generate the statistical analyses, summary tables, figures and listings to be integrated in the Clinical Study Report. The use of precise titles and footnotes will be made to improve the understanding of summaries and document any assumption. Details of analysis specifications including but not limited to the SAS code will be documented on the shells.

The final list of TLF is available in [Appendix F](#). The final mock TLF shells for the reporting of this study will be available in a separate document that will be developed and will be finalized before database lock.

18 References

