- a. In a phase 2b study for Atopic dermatitis indication (SPR.114322), a dose-dependent increase of asthma flares (1 [1.8%], 2 [3.6%], 7 [12.3%], and 10 [17.5%] in placebo, 10 mg, 30 mg, and 90 mg treatment arms, respectively) in subjects with pre-existing asthma was observed. Events were mostly mild or moderate (one severe event with highest dose), manageable, and reversible under treatment with study drug. This protocol (SPR. 204358) will exclude subjects with asthma exacerbation requiring hospitalization in the preceding 12 months before screening, subjects whose asthma has not been well controlled (i.e., symptoms > 2 days per week, nighttime awakenings two or more times per week, or some interference with normal activities) during the last three months before the screening visit, and Asthma Control Test (ACT) score ≤ 19. At all visits, all subjects will be asked about respiratory changes and a respiratory examination will be performed. At screening and baseline conduct PEF for all subjects and ACT for subjects with medical history of asthma. After baseline ACT and PEF are only required for subjects with a medical history of asthma. Subjects diagnosed with de novo asthma will perform PEF and ACT assessments at all visits starting with the visit in which the diagnosis was confirmed. Subjects with a medical history of asthma will be referred to the physician managing their asthma if ACT ≤ 19, with signs and symptoms suggestive of asthma, and/or unexpected worsening of asthma is observed or reported, PEF value is used as supplemental information. Subjects without a medical history of asthma will be referred to a respiratory specialist if respiratory changes suggestive of asthma are observed or reported. An independent adjudication committee (IAC) will review and adjudicate all asthma AEs reported during the course of the study. PEF value is used as supplemental information as well.

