Baseline is defined as the last non-missing measurement prior to the first treatment injection at Day 1/Baseline for subjects randomized and treated or prior to the randomization for subjects randomized but not treated (if any). Change from baseline and percent change from baseline are defined as follows:

$$\text{Change from Baseline} = \text{PostBaseline} - \text{Baseline}$$

$$\text{Percent Change from Baseline} = \begin{cases} \text{Baseline} \neq 0 \Rightarrow 100 \cdot \frac{\text{PostBaseline} - \text{Baseline}}{\text{Baseline}} \\ \text{Baseline} = 0 \Rightarrow \text{Missing} \end{cases}$$

All by-visit summaries and analyses will use the analysis visit (see section 4.10).

Continuous data will be summarized using the following descriptive statistics: number of subjects (n), mean, standard deviation (SD), median, first and third quartiles (Q1 and Q3), minimum and maximum. Categorical data will be summarized using the frequency count (n) and percentage (%) of subjects for each category. For the summary statistics of all numerical variables unless otherwise specified, minimum and maximum will be displayed to the same level of precision as reported. Mean, median, Q1 and Q3 will be displayed to one level of precision greater than the data collected. Standard deviation will be displayed to two levels of precision greater than the data collected.

P-values will be displayed in the following format, 0.9999. Any p-value less than 0.0001 will be displayed as <0.0001. Any p-value greater than 0.9999 will be displayed as >0.9999.

The following flagging conventions will be applied for the p-values of all statistical testing:

- $0.01 \leq p\text{-values} < 0.025$ will be flagged with one asterisk (e.g. “0.0249 *”).
- $0.001 \leq p\text{-value} < 0.01$ will be flagged with two asterisks (e.g. “0.0099 **”).
- $0.0001 \leq p\text{-value} < 0.001$ will be flagged with three asterisks (e.g. “0.0009 ***”).
- $p\text{-value} < 0.0001$ will be flagged with four asterisks (e.g. “<0.0001 ****”).

When count data are presented, the percentage will be suppressed when the count is zero in order to draw attention to the non-zero counts. The denominator for all percentages will be the number of subjects in that treatment within the analysis set of interest, unless otherwise specified. Percentages will be presented to one decimal place.

All proportions will be presented as percentages (not as fraction of unit).

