Proportion of subjects with an improvement WI NRS ≥ 4 from baseline at Week 1 will be analyzed in the ITT Set, using the Cochran-Mantel-Haenszel (CMH) test stratified by analysis center. The strata-adjusted difference in proportions of responders with 97.5% CI, pooled CMH test p-value will be derived as described in section [9.1.1](#). Subjects who took rescue therapies will be considered as treatment failures, efficacy data collected after the use of rescue therapies will be set to the worst possible value and subject's binary response will be imputed as "Non-responder". Treatment discontinuation due to lack of efficacy, AE/death related to study drug or any other reason is not a factor at this early timepoint since the second administration is not due until Week 4. Missing subject's binary response will be imputed using MI under MAR assumption (dichotomous endpoints will be calculated from the underlying imputed variable). See [Appendix C](#) for details about Multiple Imputation.

[figure not shown]
CCI

CCI

CCI

11 Immunogenicity Analyses

The immunogenicity endpoint is nemolizumab immunogenicity in adult hemodialysis subjects with moderate to severe pruritus.

Anti-drug antibodies assessments using a validated electro-chemiluminescence immunoassay (ECLIA) (screening, confirmatory, titer, Nab) and incidence of positive ADA results (absolute occurrence, percent of subject, and treatment-related ADA) will be summarized by visit and by treatment group. A treatment-related ADA is defined when at baseline, the screening or confirmatory ADA result is negative, and the post-baseline confirmatory ADA result is positive. A corresponding listing will be provided.

Summaries will be based on the Safety Set. Subjects will be summarized according to their actual treatment group.

12 Safety Analysis

Safety assessments/measurements will be conducted for all subjects at the screening visit (upon signing of the ICF) and at every subsequent visit as described in schedule of assessments in [Appendix A](#). All safety assessments/measurements will be listed in by-subject listing.

Subjects will be summarized according to their actual treatment group.

TEAEs will be summarized descriptively overall and by treatment and other safety information will be summarized descriptively by treatment.

All safety analyses will be based on the Safety Set.

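### ACT ≤ 19 percentages default to a whole-arm denominator although only subjects with asthma take the test, and post-baseline PEF summaries for subjects without asthma history would hold only newly diagnosed cases

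*SAP*

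**What the plan says.** **Who is tested.** SAP 12.9 sets out three groups.
- No asthma history: "If subjects have no asthma history, PEF will be performed at Screening and Baseline".
- Asthma history: "If subjects have asthma history, PEF and ACT will be performed at all visits according to the schedule of assessments in" Appendix A.
- New diagnosis: "If subjects have a new (de novo) diagnosis of asthma PEF and ACT will be performed at all subsequent visits".

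Protocol 8.4 agrees: "After baseline ACT and PEF are only required for subjects with a medical history of asthma". It then adds newly diagnosed subjects from the visit at which the diagnosis is confirmed. Protocol 16.8.1 gives the ACT to the same two asthma groups only.

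**What is summarised.** For ACT, SAP 12.9 plans: "For ACT, the numbers and percentages of subjects with an ACT score ≤ 19 will be summarized by visit and treatment group". For PEF it plans the share below 80% of predicted, change from baseline and classified percent change, and adds: "All PEF summaries will be presented for subjects with/without asthma history".

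**Which denominator.** SAP section 4: "The denominator for all percentages will be the number of subjects in that treatment within the analysis set of interest, unless otherwise specified". SAP section 12: "All safety analyses will be based on the Safety Set". Section 12.9 names no other base. Appendix F lists the ACT ≤ 19 table (14.3.4.9.2) on the Safety Set with no restriction. It does mark restricted populations elsewhere, for example women only (Table 14.1.2.3) and the exclusion of subjects with COVID-19 disruptions (Table 14.2.1.4.11).

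**What the protocol planned.** Protocol 19.4.7 asks only for an ACT listing, limited to subjects with asthma history.

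**The concern.** A percentage should be taken over subjects who could have shown the finding. Under the default rule the ACT denominator includes everyone dosed, most of whom never take the test, and each of them is counted as though asthma were controlled. Exclusion criterion 8c keeps out subjects with asthma history whose ACT is 19 or below at screening or baseline. An on-study score of 19 or below in that group is therefore a new crossing of the threshold, which is what this table should show.

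The PEF problem is different. The stratum without asthma history starts as a full group at baseline. After that, the only members with scheduled PEF are those who went on to develop asthma, so they are selected on the outcome. Their results would appear under a label that reads as the non-asthma group.

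Asthma matters here. Protocol 8.4 reports a dose-dependent rise in asthma flares in a phase 2b study in atopic dermatitis, Protocol 16.10 makes new or worsening asthma an event of special interest, and SAP section 15 bases dose selection on risk-benefit.

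**Working it through.** The documents state no ACT or PEF percentage and no prevalence of asthma history, so there is no planned figure to reproduce. The size can only be shown over a range.

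**Inputs**
- N = 84 per arm (SAP 4.2), assuming all are dosed and so in the Safety Set.
- p = share with asthma history. Not given; assumed 5%, 10% and 15%, with 20% as an outer value.
- x = 2 subjects with ACT ≤ 19 at a visit. Assumed, for illustration.
- No missed visits and no new diagnoses in the ACT example, for simplicity.

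**Step 1: ACT ≤ 19.** Number assessed m = N × p, rounded. The default rule gives x/N. The share of those assessed is x/m. The dilution factor is N/m and does not depend on x.

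| p | m | x/m | x/N | N/m |
|---|---|---|---|---|
| 5% | 4 | 2/4 = 50% | 2/84 = 2.4% | 21 |
| 10% | 8 | 2/8 = 25% | 2.4% | 10.5 |
| 15% | 13 | 2/13 = 15% | 2.4% | 6.5 |
| 20% | 17 | 2/17 = 12% | 2.4% | 4.9 |

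The printed 2.4% is the same in every row, although the experience of the subjects tested is quite different.

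**Step 2: PEF without asthma history.** Stratum size is 84 − m = 80, 76 or 71 for p = 5%, 10% or 15%. At baseline all of them are due for PEF, so the baseline cells can be filled properly. After baseline, scheduled PEF exists only for newly diagnosed subjects. Suppose there are 3, one of them below 80% of predicted:
- of those tested: 1/3 = 33.3%;
- of the stratum: 1/80 = 1.25%, 1/76 = 1.3% or 1/71 = 1.4%;
- of the arm: 1/84 = 1.2%.

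The first figure describes new asthma cases. The others treat at least 68 untested subjects (71 − 3) as normal. Mean change and classified percent change would rest on the same 3 subjects. No choice of denominator makes these cells describe the non-asthma group.

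**Step 3: what is not touched.** The percentages in SAP 12.1.1 for asthma-related treatment-emergent events, events of special interest and committee-adjudicated events use the Safety Set. Every dosed subject is under observation for those events, so that base is right.

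**The case against.** The strongest case against has four parts.

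**Between-arm comparison survives.** Randomisation is 1:1:1, so a base of about 84 lowers all arms about equally, and the counts are printed beside the percentages. The phase 2b flare figures in Protocol 8.4 support this: 1 (1.8%), 2 (3.6%), 7 (12.3%) and 10 (17.5%) imply bases of about 56 to 57. The peripheral edema figures from the same study imply about the same (for example 4 at 7% gives 57), so the flare percentages appear to be whole-arm, and the dose trend was plain. This stands.

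**Other outputs show the same data.** ACT is also summarised as observed values and change, with n shown. Individual plots and listings are planned, and asthma events are adjudicated. This stands, and it limits the harm.

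**The shells may settle it.** SAP section 4 allows for exceptions, and section 17 leaves analysis details to shells that cannot be seen here. This stands in part. The SAP is not silent, however: it states a default, and for ACT that default gives the wrong base. The correction belongs in 12.9.

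**For PEF the base is uncertain.** The split by asthma history may itself imply the stratum as denominator, and unscheduled PEF tests are allowed. This stands. Dilution is clear for ACT only. The PEF point rests on who is scheduled for testing after baseline.

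**Conclusion.** The point holds in a limited form. As written, the ACT ≤ 19 percentage counts never-assessed subjects as not ≤ 19. With 84 per arm and an assumed 5% to 15% with asthma history it is diluted about 6- to 21-fold, and about 5-fold at 20%. The prevalence is an assumption; the direction is not. The post-baseline PEF cells for subjects without asthma history would hold scheduled data from newly diagnosed cases only and cannot be read as the non-asthma group.

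A reader might infer more than the documents support:
- *That the asthma safety percentages in general are wrong.* Adverse-event, special-interest and adjudicated percentages are unaffected, and the ACT and PEF counts are correct.
- *That a dose-related loss of asthma control would be hidden.* Counts remain comparable between arms, and a trend would still show in them.
- *That only new cases can fill the PEF table without history.* Baseline PEF is scheduled for everyone.
- *That asthma is the main identified risk.* Protocol 8.4 lists it among the potential risks, with injection-related reactions and infections.

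These are descriptive tables with no test attached. The correction is still worth making, because the stated rule yields a misleading percentage.

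**What to change.** In SAP 12.9, and in the shells for the ACT and PEF tables:
- Use as denominator, and print, the number of subjects with a non-missing ACT or PEF at that visit, within the asthma-history stratum. For change categories, also require a baseline value.
- For subjects without asthma history, summarise PEF at baseline only.
- Present ACT and PEF of newly diagnosed subjects separately, in a labelled row or a listing, so that they stay visible as a safety outcome. Note that they have no scheduled baseline ACT, so ACT change from baseline cannot be computed for them.
- Mark the restricted population in Appendix F, as is already done for other tables.

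The cost is SAP wording and minor shell changes, with no new data and no change to who is tested. The printed denominators will be small and the percentages unstable; showing the denominator makes that plain.
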